### VAS Pain

#### CONFIDENTIAL AND PROPRIETARY

This document contains information that is confidential and proprietary to Smith & Nephew PLC and Smith & Nephew, Inc. and is intended for use only by Smith+Nephew and its manufacturer. It shall not be reproduced or copied in whole or in part, nor shall the contents be disclosed by any means without prior written permission from Smith+Nephew, nor shall anyone make any use of it that is contrary to the expressed or implied wishes of Smith+Nephew.

# Statistical Analysis Plan

A Multi-center Outcomes Clinical Study of the PyroTITAN™ HRA Shoulder Implant in Humeral Head Resurfacing

Number: CP-HRA-002  
ST: ST1159  
Version: 1.0 05/Oct/2023  
Page: 16 of 19

VAS Pain scores range from 0 to 100, with higher VAS score indicates a higher level of pain. VAS Pain will be summarised at each study visit and the absolute change in VAS scores, from baseline to each study visit will also be summarised.

A paired sample t-test will be used to test changes in the scores from baseline to each post-operative visit.

## VAS Satisfaction

VAS Satisfaction scores range from 0 to 100, with higher VAS score indicates a higher level of satisfaction.

VAS Satisfaction will be summarised at each study visit. As there is no baseline assessment of VAS satisfaction no analysis for change over time will be planned.

## WOOS

There are 19 questions, each question is answered on a visual analogue scale ranging from 0 to 100. The questions are divided into four domains: Physical symptoms (max score 600), sports and work (max score 500), lifestyle (max score 500) and emotions (max score 300). The overall score ranges from 0 to 1900, with 1900 being the worst. For ease of interpretation, scores are converted to a percentage of the maximum score for each domain and overall  $[(\text{score}/\text{max score}) * 100]$ .

The WOOS score for each domain and overall will be derived for each patient at each visit and summary statistics will be presented. Change from baseline scores per domain and overall to each post-operative visit will also be presented.

A paired sample t-test on the overall WOOS score will be used to test changes in the scores from baseline to each post-operative visit. If the t-test assumptions are not met then a Wilcoxon Signed Rank test will be considered.

## Constant Murley Score

The CM score consists of 4 domains: pain (15 points), activities of daily living (ADL) (20 points), movement (40 points) and power/strength (25 points). Strength score is calculated as the highest score of the 3 attempts.

Constant-Murley score questionnaires that are incomplete for the questions used for scoring at the baseline visit will not be included in the analyses.

The total score is calculated as the sum of each score from the 4 domains and ranges from 0 to 100 points, with a higher score indicating better shoulder function.

The CM score will be derived for each patient at each visit and summary statistics will be presented. Change from baseline score to each post-operative visit will also be presented. A paired sample t-test will be used to test changes in the scores from baseline to each post-operative visit. If the t-test assumptions are not met then a Wilcoxon Signed Rank test will be considered.

# Statistical Analysis Plan

A Multi-center Outcomes Clinical Study of the PyroTITAN™ HRA Shoulder Implant in Humeral Head Resurfacing

Number: CP-HRA-002  
ST: ST1159  
Version: 1.0 05/Oct/2023  
Page: 17 of 19

## EQ-5D Quality of Life Questionnaire

The EQ-5D-3L is a standardised measure of health status developed by the EuroQol Group and provides a simple measure of general health. The EQ-5D-3L descriptive system contains 5 dimensions: Mobility, Self-Care, Usual Activities, Pain/ Discomfort, Anxiety/ Depression. The subject is asked to answer a question on each dimension on a scale comprising of 3 levels: no problems (1), some problems (2), and extreme problems (3). This decision results in a 1-digit number expressing the level selected for that dimension. The digits for the 5 dimensions can be combined in the order shown above to form a 5-digit profile (i.e. 11111 describes no problems in any dimension). This can then be cross-referenced using vendor provided "EQ-5D-3L Crosswalk Index Value Calculator" against the country of the investigator site (Country code - site ID: AU - 401, 402; GB - 403; FR - 404; SE - 406) to come up with an index value describing the respondent's health state. Higher index values indicate better health and lower index values describe worse health.

The subject responses to each dimension (categorical) and the overall EQ-5D-3L index values (continuous) will be summarized at all study visits. The change in the index value between baseline and all post-baseline study visits will also be summarised.

EQ-5D-3L index value will be assessed using repeated measures ANCOVA model, with the change from baseline index value as the dependent variable. As a minimum the model will contain terms for visit (repeated term) and baseline index value. The following terms will be added to the model using a stepwise selection procedure with an F-value to attain a significance level of 0.1: site, primary diagnosis and BMI. The p-value for the type III effects of all fixed effects terms included in the final model will be presented. The Least Square Mean (LSMean) change in EQ-5D-3L index value between baseline and all post-baseline study visits will be presented with the associated 95% confidence interval and p-value.

If the data does not satisfy the assumptions of an ANCOVA model then an appropriate non-parametric analysis will be considered such as Wilcoxon Signed Rank Test, with the Hodges-Lehmann estimate of the median change in index value presented along with the associated 95% confidence interval.

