## 3 STUDY DESIGN

The study is a post market, multi-centre prospective, non-randomized, non-comparative, open investigation.

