### 5.2 Secondary Endpoint(s)

To demonstrate postoperative functionality and radiographic performance at 2, 3, 4, 5, 8 and 10 years post treatment, as compared with pre-treatment results through:

- ASES Score improvement
- Patient satisfaction
- VAS Pain
- WOOS
- Constant Score
- EQ-5D Quality of Life Questionnaire

Radiographic and MRI requirements for success at the different time points:

- No evidence of device failure, specifically progressive migration or implant loosening
- Anatomic alignment is a criterion that may be included in the definition of success in some investigations

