# 7 STATISTICAL ANALYSIS

## 7.1 General

Smith + Nephew's Global Biostatistics group will conduct the statistical analysis for this study. Unless otherwise stated, all significance tests and hypothesis testing will be two-sided, performed at the 5% significance level. Resulting p-values will be quoted and 95% two-sided confidence intervals will be generated where appropriate. All p-values will be rounded to three decimal places, p-values less than 0.001 will be presented as '<0.001' in all tables.

Where data summaries are specified, categorical and ordinal variables will be summarized with frequencies and percentages. Continuous variables will be summarized with the following summary statistics: number of observations, mean, median, standard deviation, minimum and maximum values. All analyses will be performed in SAS 9.4 (or later).

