# Statistical Analysis Plan

A Multi-center Outcomes Clinical Study of the PyroTITAN™ HRA Shoulder Implant in Humeral Head Resurfacing

Number: CP-HRA-002  
ST: ST1159  
Version: 1.0 05/Oct/2023  
Page: 18 of 19

EQ VAS will be assessed using repeated measures ANCOVA model, with the change from baseline in EQ VAS as the dependent variable. As a minimum the model will contain terms for visit (repeated term) and baseline EQ VAS. The following terms will be added to the model using a stepwise selection procedure with an F-value to attain a significance level of 0.1: site, primary diagnosis and BMI. The p-value for the type III effects of all fixed effects terms included in the final model will be presented. The Least Square Mean (LSMean) change in EQ VAS between baseline and all post-baseline study visits will be presented with the associated 95% confidence interval and p-value.

If the data does not satisfy the assumptions of an ANCOVA model then an appropriate non-parametric analysis will be considered such as Wilcoxon Signed Rank Test, with the Hodges-Lehmann estimate of the median change in EQ VAS presented along with the associated 95% confidence interval.

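### In this single-arm study the EQ-5D and EQ VAS models hold baseline fixed, so the intervals for change from pre-treatment are too narrow and the error rate exceeds 5%, by an amount that depends on quantities the documents do not give

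*SAP*

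**What the plan says.** SAP 3 describes a "non-randomized, non-comparative, open investigation", so there is no control arm. SAP 5.2 states the aim of the secondary endpoints, including EQ-5D: "To demonstrate postoperative functionality and radiographic performance at 2, 3, 4, 5, 8 and 10 years post treatment, as compared with pre-treatment results through" the listed measures.

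For the EQ-5D-3L index, SAP 7.10 specifies a repeated-measures ANCOVA "with the change from baseline index value as the dependent variable". It adds: "As a minimum the model will contain terms for visit (repeated term) and baseline index value". Site, primary diagnosis and BMI may enter by stepwise selection at 0.1. The output is stated as: "The Least Square Mean (LSMean) change in EQ-5D-3L index value between baseline and all post-baseline study visits will be presented", with a 95% interval and a p-value. The EQ VAS paragraph has the same structure: "As a minimum the model will contain terms for visit (repeated term) and baseline EQ VAS".

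SAP 7.1 sets the error rate: "all significance tests and hypothesis testing will be two-sided, performed at the 5% significance level", and "95% two-sided confidence intervals will be generated where appropriate". The SAP does not say at which baseline value the least-squares mean is evaluated, or that its variance allows for baseline being a random quantity. ASES, WOOS, Constant-Murley and VAS pain are analysed by paired t-tests.

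**The concern.** The question in SAP 5.2 is about a mean change: follow-up mean minus pre-operative mean. Both means are estimated from the same sample, so both contribute sampling error. A least-squares mean evaluated at the sample mean baseline gives the right point estimate with complete data, namely the observed mean change. Its standard error, however, describes the change for a patient whose baseline equals that particular sample mean. The uncertainty in the baseline mean is left out.

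In a randomised comparison this does no harm, because the baseline term cancels between arms. Here nothing cancels. The EQ-5D and EQ VAS intervals would be labelled 95% with lower real coverage. They would also stand beside paired tests on other secondary endpoints that do hold their nominal level. The problem is present in the minimum model, before any optional covariate is selected.

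**Working it through.** **Inputs from the documents.** Two-sided 5% and 95% intervals (SAP 7.1); one arm (SAP 3); minimum model terms (SAP 7.10); enrolment of 387 and attrition of 10% a year (SAP 6.1).

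**Assumed inputs.** The correlation r between baseline and follow-up, and k = follow-up SD / baseline SD, are not given for either measure, so a range is shown. The least-squares mean is taken at the mean baseline of the analysis data. No optional covariates are included.

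**Benchmark.** The 5% is a nominal setting with no calculation behind it to reproduce. A simulated paired test of mean change (20,000 runs each at n=52, 135 and 387) rejects a true null 4.8% to 5.3% of the time.

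**Formulas, complete data, baseline SD set to 1.**

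- Variance the model reports: proportional to k²(1−r²).
- True variance of the mean change: 1 + k² − 2rk = k²(1−r²) + (1−rk)².
- SE ratio s = √[k²(1−r²) / (k²(1−r²) + (1−rk)²)].
- Actual two-sided error = 2[1 − Φ(1.96 s)].
- The two variances agree only if rk=1, that is, if the slope of change on baseline is zero.

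**Worked case, k=1, r=0.3.** Model variance 0.91; omitted term 0.7² = 0.49; ratio 0.91/1.40 = 0.65; s = 0.806; error 11.4%.

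| k | r | s | Actual error | Widening needed (1/s − 1) |
|---|---|---|---|---|
| 1 | 0.2 | 0.775 | 12.9% | 29% |
| 1 | 0.3 | 0.806 | 11.4% | 24% |
| 1 | 0.5 | 0.866 | 9.0% | 15% |
| 1 | 0.7 | 0.922 | 7.1% | 8% |
| 1 | 0.9 | 0.975 | 5.6% | 3% |
| 0.8 | 0.3 | 0.709 | 16.5% | 41% |
| 0.67 | 0.3 | 0.625 | 22.1% | 60% |
| 1.25 | 0.4 | 0.917 | 7.2% | 9% |
| 1.5 | 0.5 | 0.982 | 5.4% | 2% |

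**Simulation, one visit, n=387, k=1.** 11.0%, 10.2%, 8.8% and 6.9% at r = 0.3, 0.4, 0.5 and 0.7. Results at n=52 and n=135 are similar, so a larger sample does not cure the problem.

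**With attrition.** If a fraction f of the baseline sample remains, the omitted term becomes approximately f(1−rk)². At 10 years f = 0.9¹⁰ = 0.349. For k=1, r=0.3: 0.91/(0.91 + 0.349×0.49) = 0.842, s = 0.918, error 7.2%. For r=0.5 the error is 6.4%. Simulation of a nine-visit repeated-measures model with 10% yearly random dropout (N=387, k=1, 3,000 runs) gives 7.8%, 7.4% and 7.3% at 10 years for r = 0.3, 0.4 and 0.5. At 2 years it gives 11.8%, 10.0% and 9.4%. A second simulation with a different follow-up correlation structure gives 8.5% at 10 years for r=0.3. Together these put the 10-year error at about 6% to 9% for k=1 and r = 0.3 to 0.5.

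**Confirming the cause.** Adding the omitted baseline term back to the variance returns the error to 4.7–5.2% for one visit and 4.2–5.8% for the nine-visit model.

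**The case against.** The strongest defence is that the test is valid at 5% for a narrower question, namely change conditional on the observed mean baseline. That is true. But the SAP nowhere names that estimand, and SAP 5.2 asks for comparison with pre-treatment results. Protocol 4.0 likewise gives the purpose as a pre/post difference, and Protocol 11.9 plans t-tests for interval-level pre/post comparisons.

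A second defence is that SAP 7.10 already summarises unadjusted change at each visit. With n, mean and SD reported, a reader could compute a correct paired interval. This softens the consequence but does not correct the interval and p-value that will be reported. The Wilcoxon fallback does not help either, because it applies only if the ANCOVA assumptions fail, and they can hold perfectly while this problem is present.

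A third defence concerns weight, and it stands. These are secondary measures, success is judged on the primary endpoint, and Protocol 11.1 calls the study exploratory. If the true change is large, the null will be rejected either way.

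Stronger readings are tempting, and the documents do not support them. A reader might infer that the error rate is about double the nominal 5%. That needs r of roughly 0.3 to 0.5 with equal SDs and little dropout, and the documents supply neither r nor k. A reader might infer that every interval is materially too short. The shortfall vanishes as rk approaches 1 and shrinks at late visits. A reader might infer that the fault favours the device. The point estimate is not shown to be biased and the tests are two-sided, so certainty is overstated equally for a decline and for a gain.

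**Conclusion.** The analysis is wrong as written for the stated question. For both the EQ-5D-3L index and EQ VAS, the standard error of the reported change omits baseline sampling error. The interval is too narrow and the two-sided error exceeds 5%, except where the slope of change on baseline is zero.

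The excess cannot be fixed from the documents. With complete data it runs from barely above nominal (high r, or k well above 1) through about 9% to 13% (k=1, r = 0.5 down to 0.2), and higher still if scores are less variable after surgery. Under the SAP's own attrition it falls by 10 years. All figures assume the minimum model; the effect of site, primary diagnosis and BMI, if selected, was not computed.

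If the true change is large, the harm is under-coverage rather than a false positive: about 89% to 91% real coverage at r = 0.3 to 0.5 with k=1 and complete data. The point should be corrected, but it does not bear on the primary conclusion.

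**What to change.** In SAP 7.10, for both the EQ-5D-3L index and EQ VAS, model the score itself with the pre-operative value as one of the repeated responses. Visit then has ten levels (pre-operative plus nine post-operative), with an unstructured within-subject covariance. Report each visit-minus-pre-operative contrast with its 95% interval and p-value. In simulation (3,000 runs) this gave 4.6% to 5.5% at every visit.

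A simpler alternative keeps change as the dependent variable and drops the baseline term from the model that gives the least-squares means. In simulation (2,000 runs) this gave 3.4% to 6.2% across settings.

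The baseline-covariate model may stay as a description of which patients change most, but not as the test of change. If the conditional question is really intended, the SAP should say so and label the interval accordingly.

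The cost is SAP wording and a few lines of code, with no new data. The downside is wider intervals: about 15% to 30% at k=1 and r = 0.5 to 0.2, about 40% at k=0.8 and 60% at k=0.67 (both r=0.3), and less at late visits.

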### 7.8 Multiplicity

No adjustments for multiplicity are planned for this study.

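### Stepwise choice of site, diagnosis and BMI in the EQ-5D-3L and EQ VAS models, with LSMean weights unstated, can take 95% CI coverage below its nominal level

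*SAP*

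**What the plan says.** SAP 7.10 analyses change from baseline in the EQ-5D-3L index by repeated measures ANCOVA. The guaranteed content is small: "As a minimum the model will contain terms for visit (repeated term) and baseline index value". For the remaining covariates the rule is "The following terms will be added to the model using a stepwise selection procedure with an F-value to attain a significance level of 0.1", and the candidates are site, primary diagnosis and BMI. The EQ VAS subsection repeats the rule: "with an F-value to attain a significance level of 0.1: site, primary diagnosis and BMI".

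Two kinds of inference are taken from the selected model. For the covariates: "The p-value for the type III effects of all fixed effects terms included in the final model will be presented". For the main result, the LSMean change at each post-baseline visit "will be presented with the associated 95% confidence interval and p-value". SAP 7.1 sets the general standard: "all significance tests and hypothesis testing will be two-sided, performed at the 5% significance level". SAP 7.8 adds: "No adjustments for multiplicity are planned for this study".

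The SAP gives no level for a term to stay in the model, no sensitivity analysis with a fixed model, and no weighting of LSMeans over the levels of site or diagnosis. SAP 7.2 has non-safety endpoints analysed in both FAS and PP. SAP 6.3 and 7.14 add a 5-year interim analysis so that 2- and 5-year data can be published.

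**The concern.** The same data choose the covariates and then supply the intervals and p-values, which are reported as if the model had been fixed beforehand. In a single-arm visit mean this might seem harmless, because adding a centred covariate such as BMI hardly moves the mean. Site and diagnosis are different. Without them, the LSMean weights patients as they occur in the study. With them, and with equal weighting of levels, it becomes an average over sites or diagnoses regardless of how many patients each contributes. A p-value just above or below 0.1 then decides which mean is estimated.

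A site effect on the index is plausible by construction, since SAP 7.4 and 7.10 assign country value sets by site. At stake are the stated precision of the quality-of-life change and its consistency: FAS and PP, or the 5-year and final analyses, could report LSMeans from different models that estimate different means.

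**Working it through.** **1. Figures from the plan.** The stated figure at issue is the nominal 95% of the interval. Neither document gives a sample size for EQ-5D or EQ VAS. For patient numbers, SAP 6.1 gives 150 × 0.9^10 = 52.3, which reproduces its 52. Total enrolment is 387. Applying the same attrition to 387 (an assumption) gives 387 × 0.9^10 = 134.9, about 135. SAP 7.4 lists five sites, and protocol 5.3 lists four qualifying diagnoses.

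**2. How often irrelevant terms enter.** Each null term enters with probability about 0.1. Treating the three as independent, at least one enters with probability 1 − 0.9³ = 0.271. If a null term's p-value is uniform below 0.1 once it has entered, half of such terms (0.05/0.10) will show p<0.05 in the type III table.

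**3. How far the target can move.** Group shares are not in the documents. Assume site shares of 45/25/12/10/8% and diagnosis shares of 70/12/12/6%. Equal weighting gives each site 20%, so the 8% site counts 20/8 = 2.5 times its share. Each diagnosis gets 25%, so the 6% group counts 25/6 = 4.2 times. With site and diagnosis effects of 0.1, 0.2 and 0.3 SD, the patient-weighted and equal-weighted means differed by 0.059, 0.117 and 0.176 SD. At n=135 with no site or diagnosis effects, the baseline-only CI had a half-width of 0.342/2 = 0.171 SD.

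**4. Coverage after selection.** Simulation settings, all assumed beyond the SAP's rule:
- five visits (one at n=52), within-subject correlation 0.5, no missing data;
- baseline always in the model; entry and stay at F-test p<0.1;
- BMI slope 0 to 0.2;
- 2,500–4,000 replicates per setting (Monte Carlo SE about 0.4 points near 95%, up to 0.7 at the lowest coverage).

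With unequal groups, equal-weight LSMeans and the equal-weighted mean as target:

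| Site and diagnosis effects | n=52 | n=135 | n=150 | n=387 |
|---|---|---|---|---|
| 0.1 SD | 91.0% | 90.6% | 90.2% | 89.5% |
| 0.2 SD | 87.6% | 88.8% | 89.6% | 93.8% |
| 0.3 SD | 84.7% | 93.0% | 93.3% | 94.7% |

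With no site or diagnosis effects, coverage was 92.1–93.8%. The model with all three terms forced in covered 94.6–95.5% for the same target, so the loss in the table is due to selection. It is worst when entry is uncertain: at n=135 and 0.2 SD, site entered in 69% of replicates and diagnosis in 51%. At n=387 and 0.3 SD all terms entered essentially always, and the loss nearly disappears.

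**5. Conditions that remove the loss.**
- Observed-margin weights, patient-weighted target, stepwise retained: 93.1–95.2%. The 93.1% is at n=387 and 0.3 SD, where every term entered, so it is not a selection effect.
- Equal-size sites and diagnoses, equal weights: 95.0–95.6%.
- Visit and baseline only, unequal sites, patient-weighted target: 94.0–95.6%.

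**6. Two effects to keep apart.** Scored against the patient-weighted mean, the equal-weight stepwise LSMean covered as little as 33.6% (n=387, 0.3 SD). The fixed model with all terms and equal weights also covered 33.6% there. That gap is a mismatch between weights and target, and it should not be charged to selection.

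**7. Precision.** At n=150 with no site or diagnosis effects, mean CI width was 0.328 SD for baseline only, 0.337 SD for stepwise with equal weights, and 0.478 SD with all terms forced in and equal weights (0.478/0.328 = 1.46 times baseline only). In a separate one-visit simulation at n=150 with no effects, all terms forced in with observed margins gave 0.322 SD, the same as baseline only. Over n=135–387 and site effects of 0 to 0.2 SD, that model covered 93.8–95.9%.

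**The case against.** A reader might infer that stepwise selection by itself pushes coverage below 95% whatever the circumstances. The documents do not support that. The loss needs three things together: unequal groups, equal weighting of levels, and site or diagnosis entering the model. The SAP states no weights, and neither document gives group shares.

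The weighting can also be said to be the real culprit. In a one-visit simulation with site differences up to 0.04 on an SD of 0.2 and the patient-weighted mean as target, stepwise with observed margins covered 94.3–96.1%. Stepwise with equal weights covered 89.9–93.3%, and forced-in terms with equal weights 91.5–95.4%. Stating observed margins therefore repairs coverage even with stepwise kept, and removing stepwise while keeping equal weights does not fully do so. This stands, and it is why the fix must cover both.

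A second tempting inference is that the p-values for the quality-of-life change are shown to be too small. Type I error for the LSMean change was not simulated, so that is not shown. The type III p-values are affected, but they concern covariates and no study conclusion rests on them.

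It also stands that the candidate terms, test and threshold are pre-specified, which leaves little analyst discretion. The SAP separately summarises unadjusted change from baseline at every visit for both outcomes, so the patient-weighted mean is visible whichever model is selected. The protocol calls the study exploratory, and no success criterion attaches to EQ-5D or EQ VAS. These points limit the importance. They do not justify presenting a data-selected model's interval as an ordinary 95% CI when a fixed model is as precise.

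**Conclusion.** The point holds in conditional form. The covariates are selected from the data at 0.1 in both models, the results are reported as if the model were fixed, and the LSMean weights are unstated. With unequal groups and equal weighting, coverage of the nominal 95% CI can fall to about 85–94%. With observed margins or balanced groups it stays near 95%. The range rests on assumed group shares, effects of 0 to 0.3 SD, a within-subject correlation of 0.5 and complete data; attrition-driven missingness was not simulated and could change it. Whether the shortfall would occur in this study cannot be settled from the documents, but nothing in the SAP rules it out.

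The post-selection status of the type III p-values does not depend on the weighting. Different models for FAS and PP, or for interim and final, are possible but not shown to alter any conclusion. The change is worth making, but its reach is limited to two secondary outcomes. The primary endpoint and the ASES, WOOS, Constant and VAS pain analyses use no selection.

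**What to change.** In both the EQ-5D-3L and EQ VAS subsections of SAP 7.10:
- Delete the stepwise step. Specify visit, baseline value, site, primary diagnosis and BMI as fixed terms.
- Set in advance a rule for pooling small sites and rare diagnoses, so that the same model can be fitted in FAS and PP and at interim and final.
- State that LSMeans use observed margins, and that the target is the mean change in the study's patient mix.
- If a stepwise model is still wanted, label it exploratory and do not draw the reported CI from it.

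The cost is SAP wording and, before pooling, (5−1) + (4−1) + 1 = 8 degrees of freedom if diagnosis is coded in the protocol's four categories. With observed margins, CI width was unchanged in the simulation at n=150. Forcing the terms in under equal weights would widen the interval, so the weighting statement should not be left out.
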